6.2.3 Analysis of Further Exploratory Efficacy Variables

Other exploratory efficacy variables will be as follows:

- Time to first CV hospitalization
- Total number of CV hospitalizations
- Time to first all-cause hospitalization
- Total number of all-cause hospitalizations
- Time to first occurrence of the following composite endpoint: CV death or non-fatal CV event (i.e. non-fatal myocardial infarction, non-fatal stroke, or HHF)
- Time to first occurrence of the following composite endpoint: sustained decrease in eGFR $\geq 57\%$ relative to baseline over at least 4 weeks, or sustained eGFR decline < 15 ml/min/1.73m² or initiation of dialysis or renal transplantation
- Change in eGFR from baseline
- Mean rate of change in eGFR slope and its subcomponents acute and chronic slope
- Change in UACR from baseline

- Days alive and out of hospital (DAOH)
- Time to new onset of atrial fibrillation
- Change in health-related quality of life summary scores from baseline measured by KCCQ and EuroQol Group 5-dimension 5-level questionnaire (EQ-5D-5L)

Exploratory time-to-event variables will be analyzed using the stratified log-rank test and the stratified Cox proportional hazards model. Plots of Aalen-Johansen estimates of the cumulative incidence function will be provided.

The total number of CV hospitalizations will be analyzed using an LWYY model, similarly to the primary efficacy endpoint, and will be summarized descriptively by treatment group together with the annual rate of CV hospitalizations. These summaries and analyses will be repeated for all-cause hospitalizations.

The absolute change from baseline in eGFR at each visit until Visit 10 (Month 24) will be analyzed by a repeated measures mixed model with the factors treatment group, baseline eGFR, visit, treatment-by-visit interaction, baseline-by-visit interaction, and factors for the stratification levels (pooled region for stratified analyses and LVEF). Differences between the finerenone and placebo treatment groups at each visit will be calculated, and corresponding two-sided 95% CIs will be computed. For each treatment group a separate covariance pattern will be estimated based on an unstructured covariance to adjust for the within participant variance. Change in logarithmized UACR from baseline will be analyzed in an identical fashion. Results will be back-transformed to the original scale so that ratios will be displayed in table outputs.

Frequency tables will be generated for the number and percentage of patients with a relative decrease in eGFR of $\geq 25\%$, $\geq 30\%$, $\geq 40\%$, $\geq 50\%$ and $\geq 57\%$ from baseline. The analysis will be performed for each visit and for any time post-baseline.

The rate of change of eGFR will be compared between the finerenone and the placebo group by estimating the total eGFR slope using available assessments from baseline to planned end of the treatment period. It is assumed that changes in the mean response can be expressed in terms of a linear trend, and the treatment effect can be expressed in terms of the difference in slope between finerenone and placebo. For the analysis of the total slope, the serial change in eGFR will be modeled using a two-slope linear spline mixed-effects model in which a fixed change point will be defined to separate acute and chronic eGFR slope at Month 3 (Section 2.1 of Vonesh et al. 2019). In addition to fixed effects for the treatment, time (continuous) and treatment by time interaction, the model will include fixed effects for the stratification factors and random effects for the intercept, acute slope (baseline to Month 3), and chronic slope (Month 3 to planned end of treatment period). An unstructured covariance will be used to model the between-participant errors. Within-participant errors are assumed to be homogenous. Linear contrasts will be constructed to estimate the acute, chronic, and total slope in eGFR. LS means and differences of the acute, chronic and total eGFR slope for finerenone and placebo group will be provided with 95% confidence intervals (and corresponding p-values for the differences).

DAOH will be summarized descriptively by treatment group; the number and percentage of DAOH with respect to total potential follow-up time will be provided alongside the number and percentage of days dead and days in hospital, including breakdown into type of death. These analyses will be performed overall and separately by the stratification factors (pooled region for stratified analyses and LVEF).

DAOH will be analyzed by an ANCOVA model including potential follow-up time, treatment group, and stratification factors as fixed effects. Potential follow-up time is defined as the time from randomization up to end of study or lost to follow-up or withdrawal date, in case the patient did not complete the study.

DAOH will be analyzed once considering the total potential follow-up time and once considering only the first year of follow-up.

For the KCCQ, 3 further summary scores (physical limitation score [PLS], clinical summary score [CSS] and overall summary score [OSS]) will be derived. For the KCCQ PLS, CSS and OSS, the absolute change from baseline including measurements up to month 12 of the KCCQ TSS will be analyzed by a repeated measures mixed model including the factors treatment group, baseline, visit, baseline-by-visit interaction, and factors for the stratification levels. Differences between the finerenone and the placebo treatment groups will be calculated with two-sided 95% CIs. In addition, descriptive statistics will be presented by visit and treatment group: number of observations, number of missing values, minimum, first quartile, mean, standard deviation, median, third quartile, and maximum, including the changes from baseline. The analyses for TSS are described in Section 6.2.2.

For the EQ-5D-5L, summary scores will be calculated from the 5 dimensions according to the scoring instructions from UK and the US (refer to the EQ-5D-5L User Guide (EuroQoL Group 2013) and to the EQ-5D Value Sets (Szende et al. 2007). The values and the changes from baseline of the summary scores and the EuroQoL Group visual analogue scale (EQ VAS) will be summarized by treatment group and visit using the same descriptive statistics as for KCCQ.

6.2.3.1 Patient Global Impression of Change (PGIC) and Severity (PGIS)

A sub-population of approximately 1200 participants is being asked the following questions at baseline (PGIS only) and at Visit 4 (Month 6), Visit 5 (Month 9) and Visit 6 (Month 12):

- PGIC: the participant is asked to assess the degree of change in their HF symptoms compared to the start of the treatment using the following response options: much better, better, a little better, the same, a little worse, worse or much worse
- PGIS: the patient is asked to assess the current severity of their HF symptoms due to HF using the following response options: no symptoms, mild, moderate, severe or very severe

These questions will be used as an anchor to provide an estimate of clinically meaningful change in the KCCQ TSS. Details of the analysis have been described in a separate SAP. The analysis has been conducted on a blinded dataset and will be reported separately from the CSR.

6.2.4 Outcome Events Reported by the Investigators

Outcome events using the investigator-reported terms will be summarized by treatment group, using tables analogous to those for aEs. Only adjudicated outcome events will be used for the analysis of the primary composite endpoint. Adjudication of the secondary renal endpoint will be restricted to cases of initiation of dialysis or renal transplant. No adjudication will be done for events only included in an exploratory efficacy endpoint (e.g. non-fatal myocardial infarction) and therefore the investigator-reported events will be used in the analysis of those endpoints. An overall summary of all outcome events will be generated by treatment group.

The number of participants with all outcome events, outcome events from randomization up to 30 days after stop of study medication, post-treatment outcome events occurring more than 30 days after stop of study drug or after the EoS Visit and outcome events by maximum intensity will be summarized by treatment group using MedDRA terms grouped by Primary SOC and PT.

The incidence rate of outcome events per 100 patient-years will also be provided by treatment group using MedDRA terms grouped by Primary SOC and PT. The time under risk for the incidence rates is defined as the time from randomization until the first onset of the event or the last date of contact with the participant in case no such event is recorded.

Outcome events will be summarized separately in the CSR Section 8.2 tables.

6.3 Pharmacokinetics/pharmacodynamics

6.3.1 Pharmacokinetics

The finerenone plasma concentration versus time data collected at various study visits will be evaluated descriptively, separated by dose and visit. Plots will be prepared of all individual plasma concentrations vs. actual relative study times (time of sample collection after time of study drug administration).

Evaluation of the concentration data will be performed using Population Pharmacokinetic (PK) methods, followed by PK / Pharmacodynamic (PD) analyses. These analyses will be described in a separate Analysis Plan outside of this document and will be reported separately.

6.3.2 Pharmacodynamics

Analysis of the pharmacodynamics parameters (e.g. blood pressure, heart rate, laboratory values) will be described in detail in a separate SAP.

6.4 Safety

All analyses on safety and tolerability data will be performed in SAF.

6.4.1 Adverse Events

AEs will be coded using the latest version of MedDRA available prior to database freeze. A listing will be provided linking the original investigator terms and the coded terms. AEs will be presented grouped by SOCs and PTS.

AEs that occurred or worsened after the first dose of study drug and up to 3 days after the last dose of study drug will be considered as treatment-emergent AEs (TEAEs).

To comply with local regulatory requirements in Japan and India, certain cardiovascular disease-related outcome events will also be documented as (S)AEs in Japan and India. These will be included in the outcome event tables (see Section 6.2), and to avoid double-counting of such events, they will not be included in the adverse event summary tables or listings. Separate listings will be generated for all AEs excluded from the AE analysis due to double reporting in Japan and India, respectively.

An overall summary of all AEs, pre-treatment AEs, post-treatment AEs occurring more than 3 days after stop of study drug and TEAEs will be generated by treatment group. TEAEs and treatment-emergent SAEs will be summarized by subgroups as defined in section 4.5.6.

The number of participants with TEAEs, post-treatment AEs occurring more than 3 days after stop of study drug, treatment-emergent serious adverse events (SAEs), treatment-emergent study drug-related AEs, treatment-emergent study drug-related SAEs, TEAEs and treatment-emergent SAEs resulting in discontinuation of study drug, treatment-emergent study drug-related AEs resulting in discontinuation of study drug, treatment-emergent non-serious AEs, TEAEs and treatment-emergent SAEs by maximum intensity, drug-related TEAEs by maximum intensity, TEAEs and treatment-emergent SAE by worst outcome and drug-related TEAEs by worst outcome will be summarized by treatment group using MedDRA terms grouped by Primary SOC and PT.

Hyperkalemia and worsening of renal function are considered events of special safety interest. Hyperkalemia will be defined by MLG 'Hyperkalemia' and worsening of renal function will be defined by

- List of PTs: 'Acute kidney injury', 'Blood creatinine increased', 'Glomerular filtration rate decreased', 'Postrenal failure', 'Prerenal failure', 'Renal failure' and 'Renal impairment'
- SMQ 'Acute renal failure' (narrow search)
- SMQ 'Acute renal failure' (broad search).

An overall summary for each definition of worsening of renal function as well as for hyperkalemia will provide the number of participants once for all events and once for all treatment-emergent events by treatment group.

In addition, further safety variables listed in Section 9.4.2 of the protocol are:

- Number of participants with hospitalization for hyperkalemia
- Number of participants permanently discontinuing study intervention due to hyperkalemia
- Number of participants with hospitalization for worsening of renal function
- Number of participants permanently discontinuing study intervention due to worsening of renal function

These will be summarized for treatment-emergent events by treatment group using frequency counts and grouped by Primary SOC and PT.

Cumulative incidences based on Aalen-Johansen estimates and accounting for mortality as competing risk will be provided for the time to first treatment-emergent hyperkalemia event. For this analysis, the person-time at risk for a single participant is the number of days from first intake of study intervention until the event of interest or until the minimum of (date of death, last exposure to treatment + 3 days). Since the number of participants with hospitalization or permanently discontinuing study intervention due to hyperkalemia is very low, no cumulative incidences will be displayed for these variables.

For hyperkalemia AEs, an additional sensitivity analysis will be performed where events are defined as treatment-emergent, if the AE started or worsened after the first dose of study drug up to 3 days after any temporary or permanent interruption of study drug.

The incidence of TEAEs and treatment-emergent SAEs per 100 person-years will also be provided by treatment group using MedDRA terms grouped by Primary SOC and PT. This analysis will consider the first AE per Primary SOC or PT for a participant. Per SOC or PT, the incidence per 100 person-years will be derived as

100 * (number of participants with TE(S)AE) / (sum of time at risk).

The time at risk per patient is defined as time from first dose of study drug to last dose of study drug + 3 days (treatment-emergent), or death, if earlier, for those patients without a respective AE. For patients with AE, it is the time from first dose of study drug to AE start date. In case the AE start date is (partially) missing, the earliest possible date will be imputed; i.e. first day of a month, first month of a year, restricted to date of first study drug intake.

In case of events with different intensity within a participant, the maximum reported intensity will be used. If intensity is missing, the event will be considered as severe. If the same event is reported as both unrelated and related to the study drug within a participant, the event will be considered as related to study drug. If the drug relationship is missing, the event will be considered as being related to the study drug. Deaths and SAEs will be listed separately.

Any AEs/SAEs related to study procedure recorded after signing of informed consent but prior to randomization will be tabulated separately.

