### 8.3.6 Disease-Related Events and/or Disease-Related Outcomes Not Qualifying as AEs or SAEs

The following disease-related events (DREs) are common in participants with heart failure and can be serious/life threatening:

- Worsening of heart failure, requiring hospitalization or urgent heart failure visit
- Worsening of renal function defined as a sustained eGFR decrease of 50% or more, or 57% or more compared to baseline; sustained eGFR decline below 15 mL/min/1.73m^2; initiation of dialysis for at least 30 days or renal transplantation.
- Myocardial infarction

- Stroke
- New onset of atrial fibrillation or atrial flutter

These events are typically associated with the disease under study, and will not be reported according to the standard process for expedited reporting of SAEs even though the event may meet the definition of an SAE. In addition, they will neither be unblinded, nor reported to regulatory authorities, IECs, or investigators (see also Section 8.3.4 for details). Instead, these events will be documented only on the Outcome Event/Heart Failure pages of the eCRF and will undergo adjudication by an independent, blinded Clinical Event Committee as outlined in the CEC Charter.

Adverse events leading to death will be documented on the adverse event eCRF page and DREs leading to death will be documented on the outcome event eCRF page. All deaths will undergo adjudication.

An independent, unblinded DMC will monitor all events during the study and these DREs will also be analyzed after end of study and documented in the clinical study report. Should unexpected safety issues be identified, specific amendments will be implemented.

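### SAP 6.4.1 counts worsening renal function from AE terms, so a participant whose only renal record is an outcome-page event adds nothing to those counts

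*SAP*

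**What the plan says.** **Recording.** Protocol 8.3.6 lists renal deterioration among the disease-related events: "Worsening of renal function defined as a sustained eGFR decrease of 50% or more", with the 57% threshold, sustained eGFR below 15, dialysis lasting at least 30 days and transplantation named alongside. It then says that "these events will be documented only on the Outcome Event/Heart Failure pages of the eCRF". Protocol 8.3.1 and 9.6 repeat that such events are not reported as AEs or SAEs.

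**Counting.** SAP 6.4.1, the Adverse Events section, says that "Hyperkalemia and worsening of renal function are considered events of special safety interest". It continues that "worsening of renal function will be defined by" three alternatives: a list of seven preferred terms, and the acute renal failure SMQ in its narrow and broad forms. "An overall summary for each definition of worsening of renal function as well as for hyperkalemia will provide the number of participants"; this comes in two versions, one covering every event and the other restricted to those that are treatment-emergent. The section then takes up variables from protocol 9.4.2, including "Number of participants with hospitalization for worsening of renal function" and the matching count of permanent discontinuations. On these it says: "These will be summarized for treatment-emergent events by treatment group using frequency counts and grouped by Primary SOC and PT". No outcome-page source is named.

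**Outcome events.** SAP 6.2.4, under Efficacy, tabulates investigator-reported outcome events separately from AEs, by SOC and preferred term.

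**The concern.** The recording rule sorts renal events by severity. Milder or not-yet-sustained deterioration stays on the AE page. Events that meet the outcome definition go to another page, and the counts that the SAP singles out for special safety interest do not name that page as a source. The same holds for hospitalization and permanent discontinuation for worsening renal function, which protocol 9.4.2 lists as safety variables in their own right.

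Protocol 2.3 acknowledges that worsening renal function occurs with steroidal MRAs, so a reader of the study report will look at these counts. If they leave out a severity-selected group without saying so, the reader cannot tell how complete they are or whether the omission is balanced between arms.

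**Working it through.** No arithmetic applies: the documents give no renal event rate or expected count. The check traces each type of event from where it is recorded to every place where it is specified to be counted.

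| Event (protocol 8.3.6) | AE-term counts, SAP 6.4.1 | Laboratory counts, SAP 6.4.2 | Outcome-event tables, SAP 6.2.4 | Renal composite, SAP 6.2.2 |
|---|---|---|---|---|
| Sustained eGFR fall of at least 50% or 57% | Not a source | Yes, including sustained falls | Yes | Yes |
| Sustained eGFR below 15 | Not a source | Only within the below-30 count | Yes | Yes |
| Dialysis of at least 30 days | Not a source | No | Yes | Yes, adjudicated |
| Transplantation | Not a source | No | Yes | Yes, adjudicated |

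1. **Special-interest summary.** All three definitions work on coded AE terms. A participant whose only renal record is one of the four rows above contributes 0 to each.

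2. **Hospitalization and discontinuation.** These counts use treatment-emergent events by SOC and preferred term in the same section, so the same participant contributes 0 here too. SAP 6.2.4 splits outcome events by timing and maximum intensity and gives incidence rates, but not hospitalization or drug discontinuation. The disposition tables (SAP 4.2 and 6.1.1) give reasons for stopping, but the documents do not list the categories, so they cannot be relied on to isolate a renal outcome. Protocol 8.10 mentions hospitalization by cause only as something that may be examined. Protocol 7.1.1 names outcome events, separately from (S)AEs, as a reason for interrupting study drug, so action on drug because of an outcome event is foreseen.

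3. **Windows.** AE tables use 3 days after the last dose (SAP 6.4.1). Outcome-event tables use 30 days after stopping (SAP 6.2.4). A reader cannot add the two, both because of the windows and because one participant may be in both.

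4. **India.** The amendment history (protocol 10.8) says that country amendment IND-1 has all disease-related outcome events in India reported as (S)AEs. To avoid double counting, SAP 6.4.1 removes only certain cardiovascular ones from the AE tables. Renal outcome events from India may therefore enter the AE-based counts while the general recording rule keeps those from other countries out.

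**The case against.** The strongest reply is that little is hidden. SAP 6.4.2 counts eGFR falls of at least 50% and 57%, including sustained falls, in the safety set, with comparisons between arms. SAP 6.2.4 reports outcome events by arm in tables modelled on the AE tables. The renal composite and its components are analysed, dialysis and transplantation are adjudicated, and the DMC sees outcome events unblinded (protocol 9.6). All of this stands. A reader might infer that the worst renal cases go unreported, or are missing from every safety table; the documents do not support that.

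Overlap is also likely. A sustained fall needs confirmation at least 4 weeks later (SAP 6.2.2.1), and dialysis must last at least 30 days. At admission or at drug stop the event may not yet qualify, and an AE such as acute kidney injury or a creatinine increase may already be on file. Nothing says such a record is removed once an outcome is confirmed. This stands, and it is why the point is limited to participants with no other renal record.

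Third, exclusion is inferred: SAP 6.4.1 never says that outcome-page events are left out. But the definitions sit in the AE section and use coded terms, and outcome events are tabulated apart, so a programmer following the text would leave them out.

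Finally, keeping AE and outcome reporting apart is deliberate, and a merged count mixes different kinds of record. That is a reason to keep the AE-only row, not to omit the combined one.

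**Conclusion.** As written, the special-interest summary of worsening renal function and the protocol-listed counts of hospitalization and permanent discontinuation for it omit participants whose only renal record is an outcome-page event. Two gaps are not closed elsewhere. No specified table counts hospitalization or discontinuation for these events, and dialysis and transplantation appear in no SAP 6.4 count.

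A reader might go further and infer that the omission understates harm on finerenone. The documents do not support this: they give neither the number of participants affected nor its split by arm, so size and direction cannot be derived.

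The conclusion rests on reading SAP 6.4.1 as AE-page data only, and on protocol 8.3.6 as it stands in Amendment 2 (16 MAY 2022). The SAP cites a protocol dated 26 OCT 2022, which was not available for this check. The point concerns the completeness and labelling of safety counts, and does not affect the efficacy analyses.

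**What to change.** In SAP 6.4.1:

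- State the data source of the renal counts, and keep the AE-only row.
- Add a row by arm in the safety set for participants with an AE-defined or an outcome-page renal event. Count each participant once, and show dialysis and transplantation as separate lines.
- Name one treatment-emergent window for the combined row, since the AE tables use 3 days and the outcome tables 30.
- Extend the combined row to the hospitalization and permanent-discontinuation counts where the eCRF records the cause. Where it does not, say so beneath the table.
- State how renal outcome events also reported as (S)AEs in India are handled, so that the AE-only row follows the same rule in every country.
- Cross-refer to SAP 6.2.4 and 6.4.2.

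The cost is SAP wording, one data merge and a choice of window. The documents do not show whether the outcome pages hold cause fields for hospitalization and discontinuation, so that part depends on a check of the eCRF. The downside is a count that mixes investigator-reported AE terms with outcome-page events, which is why the two rows should appear side by side.
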